10. INTERIM ANALYSES

10.1. Overview of Interim Analyses

There will be 2 planned, nonbinding, interim analyses conducted for futility for this study, based on the first 30% of participants enrolled in the study. The first interim analysis will be conducted when the first 30% of the planned randomized participants (approximate 32 in each treatment group) reach Week 12 assessments of spleen volume and MFSAF TSS or discontinue from treatment. Based on the results of this interim analysis, the DMC may recommend to terminate the study, continue the study with no changes to enrollment, or continue the study with no further enrollment permitted until review of the second interim analysis.

The second interim analysis will be initiated when the first 30% of the planned randomized participants reach their Week 24 assessments of spleen volume and MFSAF TSS or have discontinued from treatment. The DMC may recommend to either terminate the study for futility or continue the study, based on the results of this analysis.

At the interim analyses for Week 12 and Week 24 data, MFSAF TSS will be tested for futility only if spleen volume does not cross the futility boundary.

10.2. Data Cutoff for Interim Analysis

[figure not shown]
For analyses of spleen volume reduction and MFSAF TSS, a cutoff for clinical data used in the first interim analysis will be based on the date when the first 30% of the planned randomized participants (approximate 32 in each treatment group) reach Week 12 assessments of spleen volume and MFSAF TSS or discontinue from treatment. At the second interim analysis, the clinical cutoff date will be the date when the first 30% of the planned randomized participants reach Week 24 assessments of spleen volume and MFSAF TSS or discontinue from treatment.

10.3. Derivations and Calculations for Interim Analyses

For the second analysis of futility, an HSD spending function ([Hwang et al 1990](#)) with $\gamma = 2$ and an HSD spending function with $\gamma = 1$ will be used to allocate beta spending for spleen volume and MFSAF TSS, respectively. [Figure 2](#) shows that the beta spending functions allocate minimal beta for the second interim analysis.

The first analysis of futility will use the same futility boundary as the second futility analysis, but no beta will be spent.

Figure 2: Beta Spending

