3.3. Sample Size Considerations

The primary endpoint of this study is the proportion of participants with $\geq 25\%$ spleen volume reduction from baseline to Week 24 as measured by MRI (or CT scan in applicable participants). The primary endpoint will be analyzed by the CMH test stratified by baseline (or screening, if applicable) platelet count ($\geq 100 \times 10^9/L$ vs 50 to $< 100 \times 10^9/L$ inclusive) and DIPSS risk category (high vs intermediate-2 vs intermediate-1) at randomization. Assuming a 25% response rate for ruxolitinib + parsaclisib versus 5% for ruxolitinib + placebo, to achieve a 95% power to detect a statistically significant difference with a 2-sided Type 1 error of 5%, a sample size of 212 participants is required to be randomized equally between treatment groups.

For the key secondary endpoint of MFSAF TSS, assuming a response rate of 35% (25%) with ruxolitinib + parsaclisib for participants with normal (low) platelet counts and a response rate of 15% (10%) with ruxolitinib + placebo for participants with normal (low) platelet counts, a sample size of 212 will provide 81.3% power using the CMH test given a 2-sided Type 1 error of 5%.

A test for OS will be performed when 84 deaths are observed or the last participant achieved Week 24 assessments of spleen volume and MFSAF TSS, whichever is later, using the log-rank test at a 2-sided Type 1 error level of 0.05. The log-rank test will provide 80% power to detect an HR of 0.54 with 84 deaths. Assuming a median survival time of 3.7 years for ruxolitinib + placebo and an enrollment duration of 1 year, the expected total study duration is 4 years.

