10.4. Guidelines for Decision Rules

[Table 7](#) and [Table 8](#) provide the projected stopping rules if the interim analyses are conducted at the projected number of participants.

Table 7: Interim Analysis for Spleen Volume With HSD(2)

Number of Participants	Second Interim Analysis		Final Analysis	
	64		212	
Decision Outcome	Stop for Futility	Continue to Test MFSAF TSS	Do Not Reject Null Hypothesis	Reject Null Hypothesis
Z-statistic	≤ 0.16	> 0.16	≤ 1.96	> 1.96
One-sided p-value	≥ 0.436	< 0.436	≥ 0.025	< 0.025
Parsaclisib + ruxolitinib response rate ^a	$\leq 5.9\%$	$> 5.9\%$	$\leq 12.7\%$	$> 12.7\%$

^a Assumes spleen volume response rate is 5% in ruxolitinib + placebo.

Table 8: Interim Analysis for MFSAF TSS With HSD(1)

Number of Participants	Second Interim Analysis		Final Analysis	
	64		212	
Decision Outcome	Stop for Futility	Continue	Do Not Reject Null Hypothesis	Reject Null Hypothesis
Z-statistic	≤ 0.22	> 0.22	≤ 1.96	> 1.96
One-sided p-value	≥ 0.413	< 0.413	≥ 0.025	< 0.025
Parsaclisib + ruxolitinib odds ratio (RR for 50 \times to $< 100 \times 10^9/\text{L}$, $\geq 100 \times 10^9/\text{L}$ PLT) ^a	≤ 1.08 (11%, 16%)	> 1.08 (11%, 16%)	≤ 2.37 (21%, 29%)	> 2.37 (21%, 29%)

^a Assumes TSS response rate for 50 \times to $< 100 \times 10^9/\text{L}$ inclusive and $\geq 100 \times 10^9/\text{L}$ platelet is 10% and 15% in ruxolitinib + placebo group.

Preplanned analyses of safety and efficacy will be provided to an independent DMC as specified in the DMC charter. The process by which the DMC will review data and make recommendations and decisions will be documented in the DMC charter.

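### SAP 10.3 calls the Week 24 futility spend minimal, but it is 52% and 41% of beta; the 95% and 81.3% power in 3.3 count only each endpoint's own Week 24 look

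*SAP*

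**What the plan says.** Section 3.3 sizes the trial at 212 participants on spleen response rates of 25% versus 5%, "to achieve a 95% power to detect a statistically significant difference with a 2-sided Type 1 error of 5"%. It gives 81.3% power for TSS. It names no interim look behind either figure.

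Section 10.1 plans two nonbinding futility looks at the first 30% of participants (about 32 per group), one at Week 12 and one at Week 24. At both, "MFSAF TSS will be tested for futility only if spleen volume does not cross the futility boundary". Table 7 accordingly labels a passed spleen test "Continue to Test MFSAF TSS", and Table 8 gives TSS its own outcome of stopping for futility. At Week 12 "the DMC may recommend to terminate the study, continue the study with no changes to enrollment". The third option open to the committee there is a pause in recruitment that lasts until the Week 24 look has been reviewed.

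Section 10.3 assigns Hwang-Shih-DeCani (HSD) beta spending to the second look, with gamma 2 for spleen volume and gamma 1 for TSS, and comments that "the beta spending functions allocate minimal beta for the second interim analysis". On the Week 12 look it says: "The first analysis of futility will use the same futility boundary as the second futility analysis, but no beta will be spent". Tables 7 and 8 print Week 24 bounds of Z = 0.16 (spleen) and 0.22 (TSS), each with a final bound of 1.96.

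**The concern.** With a positive gamma, HSD spending is front-loaded: the share of beta spent exceeds the share of information. That does not fit a spend described as minimal.

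The futility plan also has four tests (two endpoints at two times), and a crossing on any of them may lead to termination. A power figure that counts one of the four overstates the chance that an effective combination reaches a positive final analysis when the rules are followed. Anyone reading 95% as the power of the design as run, including the committee applying the rules, would underestimate the risk of a false stop.

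**Working it through.** **Inputs from the SAP.** Information fraction t = 0.30 (10.1); gammas 2 and 1 (10.3); total beta 5% and 18.7%, from 95% and 81.3% power (3.3); final bound 1.96 (Tables 7 and 8).

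**1. Share of beta spent.** The HSD share is (1 − exp(−γt)) / (1 − exp(−γ)).
- Spleen: (1 − e^−0.6)/(1 − e^−2) = 0.4512/0.8647 = 52.2%. Times 5 points = 2.61 points.
- TSS: (1 − e^−0.3)/(1 − e^−1) = 0.2592/0.6321 = 41.0%. Times 18.7 points = 7.67 points.

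**2. Reproducing the tables.** In a nonbinding two-look normal model with drift δ at the final analysis, the interim bound is δ√t + Φ⁻¹(spend), and δ is solved so that overall power is 1 − beta.
- Spleen: δ = 3.839; 3.839 × 0.5477 − 1.942 = 0.161 (Table 7: 0.16).
- TSS: δ = 3.005; 3.005 × 0.5477 − 1.428 = 0.218 (Table 8: 0.22).

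Taking t = 64/212 instead gives 0.17 and 0.23. Reversing the sign of gamma gives −0.49 and −0.18, which rules out the opposite convention.

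**3. What 95% and 81.3% include.** If they were powers without any look, the drifts would be 3.605 and 2.849 and the bounds 0.03 and 0.13. The printed bounds appear only when 5% and 18.7% are totals over one Week 24 look and the final analysis for that endpoint. On the implied spleen drift, power without looks is Φ(3.839 − 1.96) = 97.0%, and the spleen look brings it to 95.0%.

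**4. Adding the Week 24 TSS stop.** At the design alternative TSS crosses in 7.7% of trials. With independent endpoints, primary power is 0.950 × (1 − 0.0767) = 87.7%. With spleen-TSS correlations of 0 to 0.4 it is 87.7-88.4%.

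**5. The same on the uncorrected CMH test at the stated rates.** This test is more powerful than the drift behind the tables: the pooled Z has drift 4.08 at 25% versus 5% with 106 per arm. Exact binomial power is 99.2% without looks and 98.0% with the Week 24 spleen look. Simulation stratified by platelet group, with 50-90% of participants in the normal group and a latent spleen-TSS correlation of 0.3, gives 92-94% with both Week 24 tests.

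**6. Adding the Week 12 look.** The SAP gives no Week 12 rates and no correlation between the Week 12 and Week 24 results. I assume equal rates at both times, no dropout, and that every crossing ends the study.

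| Rules followed | Normal model behind tables | Uncorrected CMH |
|---|---|---|
| None | 97% | 99% |
| Week 24 spleen | 95.0% | 98% |
| Both Week 24 tests | about 88% | 92-94% |
| All four tests | about 80-85% | 86-90% |

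The last row uses test-statistic correlations of 0.3-0.9 between Week 12 and Week 24 (normal model) or latent correlations of 0.5-0.9 (CMH). On the normal model, a Week 12 crossing on either endpoint occurs in about 10% of trials. If a Week 12 crossing only pauses enrollment, the third row applies. TSS power with its own Week 12 and Week 24 looks is 77-80% on the normal model at correlations of 0.5-0.9, against the stated 81.3%.

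**The case against.** **The spend is small in absolute terms.** For the primary endpoint 2.6 points can fairly be called small, and Figure 2, which the sentence describes, is not shown. But 7.7 points for TSS is not small, and both shares exceed the 30% information fraction. No plot of these functions could show otherwise.

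**The looks are nonbinding.** This stands. Power is lost only when a crossing is acted on, the committee may continue the study or pause enrollment, and "The process by which the DMC will review data and make recommendations and decisions will be documented in the DMC charter". The all-four figures are therefore an upper limit on the loss for the assumed Week 12 rates, not a prediction. A reader might infer that the SAP's statement of no beta at Week 12 is false. It is not: it correctly describes how the boundary was derived. What is missing is that the look still adds type II error if followed.

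**The power basis is not identified.** This stands in part. Section 3.3 does not say how 95% was computed, and a log-odds-ratio calculation gives 95.9% without looks. That is why two bases are shown. The conclusion about which look is counted comes from the bounds, not from any statement in 3.3.

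**A harsher figure is tempting.** A continuity-corrected test gives 95.6% with the Week 24 spleen look, close to the stated 95%, and would put all-four power at 76-82%. Table 7 does not support that basis. At its bounds it prints active response rates of 5.9% and 12.7% against 5% on control. The uncorrected pooled Z gives 5.9% and 12.6%; the corrected one gives 9.2% and 13.8%.

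**Conclusion.** The description of the spend as minimal is wrong on the SAP's own numbers: 52% and 41% of beta go to a look at 30% of the information. This part needs no outside assumption.

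The stated powers are incomplete rather than miscalculated. If both Week 24 rules are followed, primary power falls short of 95% by about 7 points on the normal model, or by 1-3 points on the uncorrected CMH test. The first needs only an assumed spleen-TSS correlation; the second also needs a platelet mix. The larger shortfall with Week 12 included depends on Week 12 rates and correlations that the SAP does not give, and on every crossing ending the study.

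A reader might go further and infer that the boundaries are wrong, that type I error is affected, or that these rules caused the early termination. The documents support none of these. The bounds reproduce, the looks allow no efficacy claim, and the SAP does not give the reason for termination. No remaining analysis changes. This is a minor correction to stated design properties.

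**What to change.** - **Section 10.3:** replace the description of the spend with the figures, 52% of the 5% beta (2.6 points) for spleen volume and 41% of the 18.7% beta (7.7 points) for TSS. Keep the statement that Week 12 was allocated no beta, and add that this look contributes type II error if its boundary is followed.
- **Section 3.3:** state that 95% and 81.3% include only each endpoint's own Week 24 look. Give primary power with both Week 24 rules followed and with the Week 12 look added. State the test used, the platelet mix, the assumed Week 12 rates and correlations, and whether a Week 12 crossing counts as termination or as a pause in enrollment.
- **Unchanged:** the gammas and all boundaries.

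The cost is a few sentences and a short simulation. No analysis is rerun. The power reported with all rules followed will be lower than 95%.

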10.4. Guidelines for Decision Rules

[Table 7](#) and [Table 8](#) provide the projected stopping rules if the interim analyses are conducted at the projected number of participants.

Table 7: Interim Analysis for Spleen Volume With HSD(2)

Number of Participants	Second Interim Analysis		Final Analysis	
	64		212	
Decision Outcome	Stop for Futility	Continue to Test MFSAF TSS	Do Not Reject Null Hypothesis	Reject Null Hypothesis
Z-statistic	≤ 0.16	> 0.16	≤ 1.96	> 1.96
One-sided p-value	≥ 0.436	< 0.436	≥ 0.025	< 0.025
Parsaclisib + ruxolitinib response rate ^a	$\leq 5.9\%$	$> 5.9\%$	$\leq 12.7\%$	$> 12.7\%$

^a Assumes spleen volume response rate is 5% in ruxolitinib + placebo.

Table 8: Interim Analysis for MFSAF TSS With HSD(1)

Number of Participants	Second Interim Analysis		Final Analysis	
	64		212	
Decision Outcome	Stop for Futility	Continue	Do Not Reject Null Hypothesis	Reject Null Hypothesis
Z-statistic	≤ 0.22	> 0.22	≤ 1.96	> 1.96
One-sided p-value	≥ 0.413	< 0.413	≥ 0.025	< 0.025
Parsaclisib + ruxolitinib odds ratio (RR for 50 \times to $< 100 \times 10^9/\text{L}$, $\geq 100 \times 10^9/\text{L}$ PLT) ^a	≤ 1.08 (11%, 16%)	> 1.08 (11%, 16%)	≤ 2.37 (21%, 29%)	> 2.37 (21%, 29%)

^a Assumes TSS response rate for 50 \times to $< 100 \times 10^9/\text{L}$ inclusive and $\geq 100 \times 10^9/\text{L}$ platelet is 10% and 15% in ruxolitinib + placebo group.

Preplanned analyses of safety and efficacy will be provided to an independent DMC as specified in the DMC charter. The process by which the DMC will review data and make recommendations and decisions will be documented in the DMC charter.

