3.2. Control of Type I Error

This study defines a single primary endpoint with a single primary analysis. The study will be claimed to have achieved the primary efficacy objective when the primary endpoint shows a significant result at 2-sided alpha of 0.05 at final analysis. The key secondary efficacy endpoints will be alpha-controlled and will be analyzed only when the study has reached the efficacy objective in the primary endpoint. The key secondary efficacy variables will be tested following a fixed-sequence-testing procedure with each at the 2-sided alpha level of 0.05 in the order below. Overall survival will be tested only if MFSAF TSS is significant.

1. The proportion of participants who have a $\geq 50\%$ reduction from baseline to Week 24 in the MFSAF TSS
2. OS

Descriptive statistics will be provided for other secondary [REDACTED] endpoints.

There will be 2 planned, nonbinding, futility analyses for this study based on the first 30% of participants enrolled in the study reaching Week 12 and Week 24 assessments of spleen volume and MFSAF TSS or discontinuing from treatment. As no formal decision for efficacy will be made based on these interim analyses, no overall alpha will be spent.

An independent DMC will be assembled to monitor safety data, efficacy data, and study conduct on a regular and ongoing basis during the study. See Section 10 for details regarding the alpha-spending plan and interim analyses conducted in this study.

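### Table 8's odds-ratio and response-rate row for MFSAF TSS does not match its own Z boundaries: 1.08 is too low at the interim and 2.37 too high at the final analysis

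*SAP*

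**What the plan says.** Section 10.4 introduces Tables 7 and 8 with the statement that they "provide the projected stopping rules if the interim analyses are conducted at the projected number of participants". Table 8 covers MFSAF TSS and gives each boundary in three forms: a Z-statistic, a one-sided p-value, and a row labelled "Parsaclisib + ruxolitinib odds ratio" with response rates in brackets.

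- **Second interim analysis, 64 participants:** stop for futility at Z ≤ 0.22, one-sided p ≥ 0.413, odds ratio ≤ 1.08 (response rates 11% with low and 16% with normal platelet counts).
- **Final analysis, 212 participants:** do not reject at Z ≤ 1.96, one-sided p ≥ 0.025, odds ratio ≤ 2.37 (21%, 29%).

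The footnote assumes that the TSS response rate for low and normal "platelet is 10% and 15% in ruxolitinib + placebo group". Section 10.1 puts the interim sample at "approximate 32 in each treatment group".

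Section 10.3 extends the boundary to Week 12: "The first analysis of futility will use the same futility boundary as the second futility analysis". Section 10.1 describes the status of these looks: "There will be 2 planned, nonbinding, interim analyses conducted for futility for this study". Section 3.2 fixes the final tests of the key secondary endpoints separately, "with each at the 2-sided alpha level of 0.05 in the order below".

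**The concern.** The three forms of each boundary should describe the same point. The odds-ratio and response-rate row is the form a data monitoring committee can read most directly against observed results. If it does not correspond to the Z row, the table holds two different rules, and Section 10.4 does not say which one governs.

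The two errors run in opposite directions. At the interim, the printed odds ratio makes the futility bar look lower than Z = 0.22 implies. At the final analysis, it overstates the smallest effect that would be significant.

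**Working it through.** **Inputs.** Placebo rates of 10% (low platelets) and 15% (normal platelets), Z boundaries of 0.22 and 1.96, and odds ratios of 1.08 and 2.37 come from Table 8. There are 32 per arm at the interim (Section 10.1) and 212/2 = 106 per arm at the final (Section 3.1). The SAP does not give the share of low-platelet participants, so it is varied from 0% to 100%.

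**1. Figures that do reproduce.**
- Table 7, ordinary pooled two-proportion Z: 5.9% against 5% at 32 per arm gives 0.159 (printed 0.16). 12.7% against 5% at 106 per arm gives 1.97 (printed 1.96).
- Table 8 p-value: 1 − Φ(0.22) = 0.413, as printed.
- Table 8 Z boundary: nonbinding HSD(1) spending of beta = 0.187 at information fraction 64/212 gives 0.227 (printed 0.22).
- Table 8 rates from its odds ratios, q = OR·p / (1 − p + OR·p): 1.08 gives 10.7% and 16.0%; 2.37 gives 20.8% and 29.49%. These round to the printed 11%, 16%, 21% and 29%.

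So the odds ratios agree with the rates, and Z agrees with p. The break lies between the two pairs of rows, which rules out one mistyped figure.

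**2. A check that needs no platelet mix.** The implied standard error of the log odds ratio is ln(OR)/Z.
- Interim: ln(1.08)/0.22 = 0.350 (0.32 to 0.38 allowing for rounding).
- Final: ln(2.37)/1.96 = 0.440 (0.438 to 0.442 allowing for rounding).

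With 64 rather than 212 participants the standard error should be about √(212/64) = 1.82 times larger. Here it is smaller. Scaling the final pair back gives an interim odds ratio of exp(ln 2.37 × 0.22/1.96 × 1.82) ≈ 1.19. Scaling the interim pair forward gives a final odds ratio of exp(ln 1.08 × 1.96/0.22 ÷ 1.82) ≈ 1.46. Both printed pairs cannot be right.

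**3. Full recomputation.** With m per arm in a platelet stratum, placebo rate p, active rate q and mean p̄, the expected CMH statistic is

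Z = Σ m(q − p)/2 ÷ √[Σ m² p̄(1 − p̄)/(2m − 1)].

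Example at a 50:50 mix:
- Interim (m = 16), OR 1.08: numerator 0.138, variance 0.767 + 1.082 = 1.849, Z = 0.138/1.360 = 0.101.
- Final (m = 53), OR 2.37: numerator 6.714, variance 3.490 + 4.627 = 8.117, Z = 6.714/2.849 = 2.356.

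| Low-platelet share | Z for OR 1.08, n = 64 | OR giving Z = 0.22 | Z for OR 2.37, n = 212 | OR giving Z = 1.96 |
|---|---|---|---|---|
| 0% | 0.111 | 1.163 | 2.530 | 1.979 |
| 25% | 0.106 | 1.171 | 2.443 | 2.025 |
| 50% | 0.101 | 1.179 | 2.356 | 2.075 |
| 75% | 0.097 | 1.188 | 2.267 | 2.132 |
| 100% | 0.093 | 1.195 | 2.181 | 2.191 |

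A Wald (Woolf) log-odds-ratio calculation gives 1.162 to 1.194 and 1.989 to 2.214. Six strata (assumed DIPSS splits 30/50/20, 33/33/33 and 20/50/30, with 30% to 90% normal platelets) give 1.17 to 1.19 and 2.01 to 2.14. The printed pairs would need about 251 to 353 participants at the interim and 128 to 171 at the final.

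**4. Cross-check from the SAP's stated power.** The Section 3.3 rates give odds ratios of 3.05 (35% against 15%) and 3.00 (25% against 10%), about 3.03 overall. Power of 81.3% then implies a standard error at 212 of ln(3.03)/(1.96 + 0.889) = 0.389. The matching odds ratios are exp(0.22 × 0.389 × 1.82) ≈ 1.17 and exp(1.96 × 0.389) ≈ 2.14. If 81.3% is instead power net of futility stopping, the drift is 3.006 and the odds ratios are about 1.16 and 2.06.

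**The case against.** **The row decides nothing.** The Z and p-value rows are printed in the same table and agree. The looks are nonbinding, TSS is examined only if spleen volume passes its own futility boundary, and the final test is fixed elsewhere. All of this stands. The practical gap at the interim is also small. With 32 per arm and a 50:50 mix, the expected responders are 4.0 on placebo, about 4.3 at an odds ratio of 1.08 and about 4.6 at 1.18. In simulated interim data sets of 64, decisions by Z ≤ 0.22 and by odds ratio ≤ 1.08 differed in about 0.4% to 1.4% of trials with two platelet strata, and 0.9% to 3.5% with six strata (assumed DIPSS split 30/50/20). The trial ended early, so no changed decision is claimed.

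**The SAP does not state the variance formula, and a continuity correction narrows the final gap.** With the correction, the final odds ratio for Z = 1.96 is 2.09 to 2.35, and 2.37 gives Z = 1.99 if every participant has low platelets. Uncorrected CMH gives 82.4% to 92.5% power at the Section 3.3 rates, always above the stated 81.3%, whereas the corrected version gives 81.3% at 75% low platelets. This makes 2.37 less firmly wrong than 1.08, but it does not rescue the row. At that 75% mix the corrected odds ratios are 1.54 and 2.27, neither as printed. Across all mixes the corrected interim value is 1.44 to 1.58, further from 1.08. Table 7 reproduces without a correction.

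**Conclusion.** The odds-ratio and response-rate row of Table 8 is wrong against its own Z row. That the two pairs conflict needs no assumption beyond the usual scaling of the standard error with sample size. That 1.08 is too low and 2.37 too high holds for every platelet mix and every variance formula tried.

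Without a continuity correction, the matching values are about 1.16 to 1.20 (rates about 11.4–11.7% and 17.0–17.4%) at the interim and 1.98 to 2.21 (about 18–20% and 26–28%) at the final. The printed interim odds ratio corresponds to a one-sided p of about 0.46 rather than 0.413. The exact replacement depends on the sponsor's platelet mix and variance formula, which the SAP does not state.

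Type I error, formal power and the Z boundaries are untouched. This should be fixed because it is a misprinted threshold in the stopping table, but it does not threaten the trial's conclusions.

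**What to change.** Recompute the odds ratios and response rates in Table 8 from Z = 0.22 at 64 participants and Z = 1.96 at 212, using the sponsor's own assumed platelet mix. State that mix and the variance formula, including whether a continuity correction was used, in the footnote. As illustration only, uncorrected CMH at a 50:50 mix gives about 1.18 and 2.08. Add a sentence that the Z-statistic governs and the odds-ratio row is illustrative. Because the first interim analysis shares the boundary, any material that quoted the row for that look needs the same correction.

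The cost is one table row, one footnote and one sentence. No analysis, test or boundary changes.
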